### **Laboratory Methods:**

Within 24 hours of blood sampling, we will conduct our ektacytometric analysis. Samples will be drawn into EDTA tubes. In the clinical hematology lab, hemoglobin, hematocrit, red cell indices, and RBC number will be measured by standard methods. A blood smear will be stained with a Giemsa stain and reviewed by clinical cytologists. Ektacytometry will be performed in the CCHMC Erythrocyte Diagnostic Lab per clinical testing SOP. Specifically, a 300 microliter sample will be injected into the Osmoscan LoRRca MaxSis (Mechatronics Instruments BV, Zwaag, The Netherlands) ektacytometer. Patients' RBCs deformation will be monitored while exposed to a constant shear stress of 30 Pa and an increasing osmotic gradient in

order to generate the ektacytometry curves. A positive result is seen as a divergence of the Omin, Elmax, and Ohyp of the sample compared to a concurrently-run normal control and the normal control range for the assay. Deformability will also be tested under an increasing shear stress for further investigation of the RBC cytoskeleton mechanics. The Erythrocyte Diagnostic Lab will then discard the remaining sample once a result is obtained.

Bilirubin levels, bile acid levels, lipid profiles, and vitamin E levels will be measured by standard laboratory methods employed by the CCHMC clinical laboratory. Bile acids will be measured by radioimmunoassay.

#### Statistical analysis

We will compare the Omin and El max values between patients and controls by Student's t test of the means. The ektacytometry characteristics (mainly values of Omin and Elmax) will be correlated with direct bilirubin levels, serum cholesterol levels and vitamin E levels by linear regression analysis.

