### Design/Methods:

This pilot study will be a single center, prospective cross-sectional investigation of red blood cell ektacytometry in pediatric patients with extrahepatic cholestasis who are followed at Cincinnati Children's Hospital Medical Center. We will include all subjects with cholestasis regardless of the etiology in order to maximize the number of subjects. While the population will be heterogeneous, we will stratify patients according to diagnosis, recognizing that only a few patients may fall into each diagnostic category. Ektacytometry will be the method utilized to measure osmotic fragility and deformability of the RBC membrane. The ektacytometry of red cells from cholestatic patients will be compared to that of red cells obtained from contemporaneous age-matched controls recruited among patients without liver disease or red cell membrane defects undergoing blood sampling for evaluation of other entities including but not confined to functional abdominal pain.

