## 2. PURPOSE OF STUDY

### Primary Aim:

The primary aim is to determine if ektacytometry of red blood cells is abnormal in a population of pediatric patients over age one with cholestasis.

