### **4. STUDY DESIGN**

This pilot study will be a single center, prospective cross-sectional investigation into the ektacytometry of red blood cells taken from 20 cholestatic pediatric patients followed at Cincinnati Children's Hospital. They are seen regularly for continued follow up in the hepatology clinic. Parents of all of these patients will be asked to participate in this investigation. We will also contemporaneously analyze ektacytometry of 20 age-matched controls recruited from the general GI clinics with neither cholestatic liver disease nor known red cell membrane defects.

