### **Controls**

Age matched to disease cohort  
No evidence for cholestatic liver disease  
No known congenital red cell membrane defect

- Exclusion Criteria.

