## 7. PROCESS OF OBTAINING CONSENT

The Research Team will discuss appropriateness for study inclusion with the clinical team, and contact the family, most likely during their hepatology outpatient clinic visit or an inpatient hospitalization. The study will enroll children, a vulnerable population, therefore patients and parents will be explicitly informed that choosing not to participate, will in no way affect the quality of the medical care that they will receive.

Details of the study will be reviewed with one or both parents prior to obtaining consent. All patients will be under the age of 18 years old and therefore only parental consent will be necessary along with the participant's assent if older than 11 years of age.

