## **8. STUDY PROCEDURES**

All patients are routinely seen in outpatient clinic by one of the hepatologists from Cincinnati Children's Hospital Medical Center. Control patients will be gastroenterology patients seen by one of the general gastroenterologists in the general gastroenterology clinics. The research team will approach the family in clinic or in the hospital and after informed consent will obtain a 500-1500 mcl aliquot left-over from blood that has been drawn into a lavender top (EDTA) tube for measurement of a complete blood count. or a yellow top tube for measurement of serum chemistries. To avoid research-only blood draws, blood will only be obtained if the patient is undergoing clinical laboratory testing. The team's PI, [name], and coinvestigators, [name] and [name], will have access to the individual results of the assay.

All blood samples will be de-identified with the assigned research number.

In addition to providing a blood sample, we will record in a secure database the patient's demographics such as current age at time of blood draw, race and ethnicity, birth history, past medical and surgical history as well as contemporaneous direct bilirubin levels, hemoglobin levels, hematocrit levels, and red cell morphologic changes noted in the hemogram. Cholesterol levels, bile acid levels, and vitamin E levels which were obtained as close as possible to the ektacytometry analysis will also be recorded. Only the investigators at Cincinnati Children's will have access to this database.

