## **9. DATA ANALYSIS/METHODS**

### **Sample size:**

The sample size of 20 cholestatic patients and 20 controls is estimated based on the number of patients followed at CCHMC. We estimate a 75 % participation rate for the study. Knowing that we have a small patient pool within each diagnostic category of cholestatic patients, we will stratify patients according to diagnosis, but suspect that we will have only 3-5 patients within each diagnostic grouping, so it may be difficult to draw conclusions regarding relative differences in osmotic fragility and deformability within the overall cholestatic population. Because this is a pilot study we do not know what the difference in Omin or deformability between patients and controls will be. Hence we cannot conduct power analysis. However, we can utilize our preliminary data to facilitate power analysis for future studies.

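### Controls are matched on age and age is recorded, but the group comparison is a plain t test that ignores age, so precision and power are lost if age relates to Omin or Elmax.

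*Protocol*

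**What the plan says.** Age matching is stated in three places in the protocol. The abstract (Design/Methods) describes "contemporaneous age-matched controls recruited among patients without liver disease or red cell membrane defects", section 4 plans "20 age-matched controls recruited from the general GI clinics", and the control inclusion criteria in section 6 read "Age matched to disease cohort". None of them says whether matching is individual or by frequency, or gives a tolerance.

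The age range is wide. The disease cohort must be older than one year (section 6), and section 7 sets the upper end: "All patients will be under the age of 18 years old". Section 8 lists "current age at time of blood draw" among the recorded data.

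The primary aim in section 2 is: "The primary aim is to determine if ektacytometry of red blood cells is abnormal in a population of pediatric patients over age one with cholestasis". The between-group analysis, in section 9 (Statistical analysis), is: "We will compare the Omin and El max values between patients and controls by Student's t test of the means". The regression named next covers bilirubin, cholesterol and vitamin E, not age. Section 9 (Sample size) fixes 20 patients and 20 controls by availability, says no power analysis is possible, and adds that "we can utilize our preliminary data to facilitate power analysis for future studies".

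**The concern.** Age decides who becomes a control and then disappears from the analysis. With matched groups, the age contribution to the two means largely cancels, so the difference in means varies less from sample to sample than an unmatched difference would. The two-sample t test cannot see this. It estimates its standard error from the full spread within each group, age included. If age matters, the standard error is too large.

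The sample is small and cannot easily grow, so the analysis is one of the few places where precision can still be gained. Two lesser points follow. An age term would also correct any imbalance that loosely defined matching leaves. And if the SD carried into later power calculations still contains age variation, the next study would be planned larger than an age-adjusted analysis needs.

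**Working it through.** The protocol states no effect size, SD or power, so there is no figure of its own to reproduce.

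**Inputs from the protocol:** n = 20 per group (section 9); ages from above 1 to under 18 years (sections 6 and 7).

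**Assumptions, not in the protocol:** two-sided alpha 0.05; within-group SD = 1; ages uniform on 1–18; a linear age effect explaining a share R² of within-group variance; true difference 0.8 SD for power.

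**Step 1, interval half-width, in SD units**

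- Plain t test (38 df): t × √(2/20) = 2.024 × 0.3162 = 0.640.
- Linear model with age (37 df, ages balanced by matching): 2.026 × √((1 − R²) × 2/20).

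| R² | Age-adjusted half-width | Ratio to 0.640 |
|---|---|---|
| 0 | 0.641 | 1.001 |
| 0.1 | 0.608 | 0.950 |
| 0.2 | 0.573 | 0.895 |
| 0.3 | 0.536 | 0.837 |

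**Step 2, why the plain test is conservative**

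Under exact matching the true standard error is √(1 − R²) times the one the t test uses. Rejecting at 2.024 is therefore roughly like rejecting at 2.024/√(1 − R²). At R² = 0.3 this is 2.024/0.837 = 2.42, for which the two-sided tail on 38 df is about 2%.

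**Step 3, simulation (40,000 data sets per setting)**

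Exact age matching:

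| R² | Type I error, t test | Power, t test | Power, age-adjusted |
|---|---|---|---|
| 0 | 4.9% | 69.5% | 69.5% |
| 0.1 | 3.8% | 70.0% | 73.6% |
| 0.2 | 2.8% | 71.3% | 78.5% |
| 0.3 | 2.0% | 72.9% | 84.3% |

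The age-adjusted model holds type I error at 4.8–5.0%. Frequency matching in three age bands (1–5, 6–11, 12–17) gives nearly the same picture. At R² 0, 0.1, 0.2 and 0.3:

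- type I error of the t test is 5.0%, 4.0%, 3.2% and 2.3%;
- power is 69.2%, 70.1%, 71.1% and 71.9% for the t test, against 69.1%, 73.7%, 78.6% and 83.7% adjusted;
- the width ratio is 1.002, 0.951, 0.897 and 0.838.

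A larger true difference gives the same pattern. At 0.909 SD, where an ordinary t test has 80% power, power is 81% against 84% at R² = 0.1 and 84% against 92% at R² = 0.3.

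**Step 4, paired t test as the alternative**

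With 19 df the critical value is 2.093. At R² = 0 the width ratio is 2.093/2.024 = 1.034 from critical values (1.027 simulated), so pairing costs about 3% if age is irrelevant.

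**Step 5, secondary quantities**

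- The SD of uniform ages on 1–18 is 17/√12 = 4.91 years. A leftover mean age gap of 2 years would shift the unadjusted difference by 2 × √R²/4.91 = 0.13, 0.18 or 0.22 SD at R² 0.1, 0.2 or 0.3.
- A future study sized on the unadjusted SD is 1/(1 − R²) = 1.11, 1.25 or 1.43 times the size an age-adjusted analysis needs.

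**The case against.** The best defence is that the planned test is valid. It does not inflate false positives, matching still guards against age confounding, and the protocol promises no power that could be missed. A simple test in a 20 versus 20 pilot could be called a matter of taste. Nothing in the document says Omin or Elmax changes with age after the first year; the laboratory section mentions no age-specific reference range. The loss is negligible at R² of 0.05 or less. The t test's power does not fall as R² rises; it is low only beside the adjusted analysis. All of this stands, and it is why the point is conditional and of moderate weight.

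It could also be said that pairing and covariates are details for the SAP, and that Student's test has a paired form. This is weaker. Section 9 names the method, so the criticism is of a stated choice. A comparison of group means reads as two-sample, and no 1:1 pairing is described anywhere.

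The two secondary arguments are fairly discounted. No 2-year age gap is suggested by the document, and since age is recorded, an age-adjusted SD could be computed later whatever test is used now. The main point does not rest on either.

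**Conclusion.** The concern holds, as a conditional loss of precision. The protocol matches on age, records it, and then specifies a comparison that leaves it out. Over an assumed R² of 0.1 to 0.3, the adjusted interval is about 5% to 16% narrower. Power at 0.8 SD is higher by about 4 points at R² = 0.1 and 11 to 12 points at R² = 0.3. The plain test's type I error falls to between 4.0% and 2.0%. At R² = 0 nothing is lost either way. These sizes rest on the assumed R², uniform ages, a linear age effect and two-sided alpha 0.05; the protocol gives none of them. The change should be made because the possible gain is material and the cost is close to nil.

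**What to change.** In section 9, Statistical analysis, replace the t test sentence with wording such as: *Omin and Elmax will be compared between patients and controls by a linear model with group and age at blood draw as terms, reporting the adjusted difference with its 95% confidence interval.*

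This works whether matching turns out to be individual or by frequency, and it handles leftover imbalance. A paired t test should not be the default, because it needs 1:1 pairs that the protocol does not describe.

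The cost is one sentence and one degree of freedom (38 to 37). No extra patients, blood or data are needed.

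### The pooled-variance Student's t test for Omin and Elmax can exceed its nominal type I error if the cholestatic group ends up both smaller and more variable than the controls; Welch's test removes the risk at almost no cost

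*Protocol*

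**What the plan says.** The primary aim (section 2) is to find out whether ektacytometry is abnormal in children with cholestasis. The only between-group test named for it is in section 9, Statistical analysis: "We will compare the Omin and El max values between patients and controls by Student's t test of the means". No significance level, variance check or unequal-variance version is given.

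On group sizes, section 9 states: "The sample size of 20 cholestatic patients and 20 controls is estimated based on the number of patients followed at CCHMC". It adds: "We estimate a 75 % participation rate for the study". Section 4 plans the same number of controls: "We will also contemporaneously analyze ektacytometry of 20 age-matched controls recruited from the general GI clinics".

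On spread, the Design/Methods part of the abstract says: "While the population will be heterogeneous, we will stratify patients according to diagnosis". Section 6 sets a lower limit for direct bilirubin in the disease cohort and no upper limit. The controls are also of mixed indication; they are children "undergoing blood sampling for evaluation of other entities including but not confined to functional abdominal pain". No SD for Omin or Elmax appears anywhere, and on the size of the effect the protocol says: "Because this is a pilot study we do not know what the difference in Omin or deformability between patients and controls will be".

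**The concern.** Student's test estimates one common variance and weights each group's sample variance by its degrees of freedom. When the smaller group has the larger variance, that estimate leans towards the less variable group. The standard error of the mean difference is then too small, the p-value too low and the confidence interval too narrow.

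Two features of the design make this worth checking. The patients span several diagnoses and an open-ended range of severity, and the secondary aim supposes that Omin and Elmax move with bilirubin, cholesterol and vitamin E. If they do, spread in those markers adds to the patient variance, and controls without cholestasis lack that source. In addition, the target of 20 patients rests on the number followed at the centre, with 75% expected to take part, so the patient group could fall short. If both things happen, ektacytometry would be called abnormal more often than the nominal level allows. The interval passed on to plan future studies would also be too narrow.

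**Working it through.** There is no plan figure to reproduce, because the sample size is set by availability and the protocol gives no significance level, SD, effect or power.

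**Inputs**
- From the protocol: Student's t test; 20 patients and 20 controls; 75% participation.
- Assumed: two-sided 5%, normal data, independent groups, equal means, patient/control SD ratio r from 0.5 to 3 (control SD set to 1).
- Group sizes: 20/20 as planned. If 20 is the pool before refusals, 20 × 0.75 = 15, which gives 15/20 if only patients fall short and 15/15 if both groups do. If 20 is the number after refusals, 20 / 0.75 = 26.7, so 27 would be approached and 20/20 stands. 18/20 shows a mild shortfall.

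**Step 1: the standard error**

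True variance of the mean difference: r²/n₁ + 1/n₂.

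Expected value of the pooled estimate: [((n₁−1)r² + (n₂−1)) / (n₁+n₂−2)] × (1/n₁ + 1/n₂).

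- 15/20, r = 2: true 4/15 + 1/20 = 0.3167; pooled (14×4 + 19)/33 × (1/15 + 1/20) = 2.2727 × 0.11667 = 0.2652. The pooled SE is √(0.2652/0.3167) = 0.915 of the true one, about 8.5% too small.
- 15/20, r = 1: both equal 0.1167, so there is no bias.
- 15/20, r = 0.5: true 0.25/15 + 1/20 = 0.0667; pooled (14×0.25 + 19)/33 × 0.11667 = 0.0795. The SE is about 9% too large.
- 20/20, r = 2: true 4/20 + 1/20 = 0.25; pooled (19×4 + 19)/38 × 0.1 = 0.25. There is no bias; only the degrees of freedom are slightly off.

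**Step 2: type I error by simulation** (400,000 or more draws per setting; repeat runs differ by about 0.1 percentage point)

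| Patients/controls | r = 0.5 | r = 1 | r = 1.5 | r = 2 | r = 3 |
|---|---|---|---|---|---|
| 20/20, Student | 5.2% | 5.0% | 5.1% | 5.2% | 5.5% |
| 18/20, Student | 4.6% | 5.0% | 5.6% | 6.0% | 6.6% |
| 15/20, Student | 3.5% | 5.0% | 6.4% | 7.5% | 8.7% |
| 15/15, Student | 5.3% | 5.0% | 5.1% | 5.4% | 5.6% |

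Welch's test uses SE = √(s₁²/n₁ + s₂²/n₂) and df = (s₁²/n₁ + s₂²/n₂)² / [(s₁²/n₁)²/(n₁−1) + (s₂²/n₂)²/(n₂−1)]. It stayed between 4.9% and 5.2% in every setting tried, including 10/20 with r = 3.

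For normal data the same error carries over to the confidence interval. At 15/20 and r = 2, a nominal 95% pooled interval covers about 100 − 7.5 = 92.5%.

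**Step 3: cost of Welch when the variances are equal**

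Mean df is 36.3 against 38 at 20/20 (about 2 lost) and 29.4 against 33 at 15/20 (about 4 lost). The power loss was below 0.5 percentage points at both sizes.

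**The case against.** The strongest reply is that the protocol plans equal groups, and there Student's test is robust: at most about 5.5% even with a threefold SD ratio. That stands. So does the point that age-matched control recruitment may shrink both groups together, which at 15/15 leaves the rate at 5.0% to 5.6%.

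A reader might infer that the false-positive rate is too high whenever fewer patients than controls are obtained. The calculation does not support this: at 15/20 the rate is nominal with equal SDs and 3.5% when the patient SD is half the control SD. Inflation needs both conditions.

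A reader might also infer that the protocol itself expects the larger SD in patients. It does not say so. Its remark on heterogeneity concerns diagnosis, and the controls are mixed too. Nor does the 75% figure make 15/20 the expected outcome: it is given for the study as a whole, and the text does not say whether 20 is counted before or after refusals.

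Finally, variance handling is often left to an analysis plan, and none is shown here. Here, though, the protocol names the test itself, so the choice is already made.

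**Conclusion.** The point holds as a conditional, minor one. The test the protocol fixes is anti-conservative if the cholestatic group is both smaller and more variable: about 6.4% to 8.7% at 15/20 and 5.6% to 6.6% at 18/20, for SD ratios of 1.5 to 3. At the planned 20/20 the departure is negligible. These figures rest on an assumed two-sided 5% level, normal data, independent groups and assumed SD ratios, none of which the documents supply. The reason to act is that the two conditions cannot be ruled out beforehand, that choosing a test after seeing the variances is open to criticism, and that the alternative costs almost nothing.

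**What to change.** In section 9, Statistical analysis, replace the words "by Student's t test of the means" with: *by Welch's unequal-variance t test, reported with the mean difference and its 95% confidence interval*.

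The change is one phrase and needs no further data or patients. Its only statistical price falls due if the variances are equal: about 2 degrees of freedom at 20/20 and 4 at 15/20, less than half a percentage point of power.

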### Objective:

We propose to perform ektacytometry on 20 pediatric patients over age one with cholestatic liver diseases and a direct bilirubin level of greater than 2 gm/dl. The most common diagnoses will be extrahepatic biliary atresia, progressive familial intrahepatic cholestasis, Alagille syndrome, autoimmune hepatitis, primary sclerosing cholangitis, and parenteral nutrition-associated cholestasis. We will correlate the osmotic fragility and deformability with their direct bilirubin levels, their serum cholesterol levels, their serum bile acid levels, and their vitamin E levels.

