### **Secondary Aims:**

The secondary aim is to ascertain the extent at which abnormalities in bilirubin levels, bile acid levels, vitamin E levels or cholesterol levels in cholestatic patients are related to changes in red blood cell ektacytometry in this patient population.

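### Stratification by diagnosis is promised but given no role in the secondary regressions, so a slope across all 20 patients is a crude association that can partly or wholly reflect differences between diseases.

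*Protocol*

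**What the plan says.** The Abstract (Design/Methods) explains why the cohort is mixed: "We will include all subjects with cholestasis regardless of the etiology in order to maximize the number of subjects". It continues: "While the population will be heterogeneous, we will stratify patients according to diagnosis, recognizing that only a few patients may fall into each diagnostic category". The Abstract (Objective) names six diagnoses: "The most common diagnoses will be extrahepatic biliary atresia, progressive familial intrahepatic cholestasis, Alagille syndrome, autoimmune hepatitis, primary sclerosing cholangitis, and parenteral nutrition-associated cholestasis".

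Section 9 (Sample size) repeats the commitment: "we will stratify patients according to diagnosis, but suspect that we will have only 3-5 patients within each diagnostic grouping". It then warns that conclusions about relative differences within the cholestatic group may be difficult.

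Section 9 (Statistical analysis) is the only place where the method is fixed. The ektacytometry values, mainly Omin and Elmax, "will be correlated with direct bilirubin levels, serum cholesterol levels and vitamin E levels by linear regression analysis". It mentions neither diagnosis nor strata. The Abstract (Objective) and Section 3 describe the correlations in the same way.

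The secondary aim in Section 2 is to find how far abnormal laboratory levels "in cholestatic patients are related to changes in red blood cell ektacytometry in this patient population".

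**The concern.** The protocol treats diagnosis as important enough to stratify on, then gives a regression in which it does not appear. The reader cannot tell what the strata are for.

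This matters because the six named diseases are quite different. Suppose one has both high cholesterol and an Omin shifted for some unrelated reason. A line through all 20 points will then slope even if, among children with the same disease, cholesterol and Omin are unrelated. Sections 1 and 3 propose a mechanism running from cholestasis through cholesterol to the red cell membrane, so a reader will be inclined to take such a slope as support for it. Section 9 also says the data will serve to plan later studies, so a slope driven by the disease mix would be carried forward.

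**Working it through.** **The plan's own figure.** There is none to reproduce. The 20 patients and 20 controls come from the number followed at the centre, and Section 9 declines a power analysis.

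**Inputs from the protocol.** There are 20 cholestatic patients with 3-5 per diagnosis, so 20/5 = 4 to 20/3 = 6.7 groups, that is, about 4 to 6. Six diagnoses are named.

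**Assumptions.** The protocol gives neither a significance level nor the share of variance due to diagnosis. I took two-sided 5% and varied the share.

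**Step 1: are separate regressions per stratum possible?** With n patients a slope has n - 2 residual degrees of freedom (df), and the smallest significant correlation is |r| = t/√(t² + df).

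| Patients in stratum | df | t | smallest significant \|r\| |
|---|---|---|---|
| 3 | 1 | 12.706 | 0.997 |
| 4 | 2 | 4.303 | 0.950 |
| 5 | 3 | 3.182 | 0.878 |

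They are not workable. If the strata are to inform the regressions, it must be in another way.

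**Step 2: test of the slope without a diagnosis term.** For each patient, predictor and outcome were each generated as a diagnosis effect plus an individual effect, with total variance 1. The diagnosis effects of the two variables were independent, and the slope within diagnoses was zero. Each setting had 20,000 simulated data sets. The table gives the percentage rejected at nominal 5%.

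| Share of variance due to diagnosis, both variables | 6 groups of 3-4 | 5 groups of 4 | 4 groups of 5 |
|---|---|---|---|
| 10% | 5.4 | 5.1 | 5.4 |
| 20% | 6.1 | 6.4 | 6.3 |
| 30% | 7.0 | 7.8 | 8.3 |
| 50% | 11.7 | 13.2 | 15.0 |
| 70% | 19.1 | 23.0 | 26.5 |

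If diagnosis explains 50% of one variable and none of the other, the rate is 4.8-5.3%, so there is no inflation. With a common slope and a separate intercept per diagnosis, the rate is 4.6-5.2% in every setting.

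**Step 3: diagnosis means that move together.** With five groups of 4 and a zero slope within diagnoses, the mean pooled slope is 0.12 (share 30%, correlation of diagnosis means 0.5). It rises to 0.33 (share 50%, correlation 0.8). Rejection runs from 11% to 36%. Here the slope itself is displaced as an estimate of the within-diagnosis relation.

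**Step 4: cost of diagnosis intercepts.** With k diagnoses, df = 20 - k - 1.

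| Model | df | t | smallest significant \|r\| |
|---|---|---|---|
| No diagnosis term | 18 | 2.101 | 0.444 |
| 4 intercepts | 15 | 2.131 | 0.482 |
| 5 intercepts | 14 | 2.145 | 0.497 |
| 6 intercepts | 13 | 2.160 | 0.514 |

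The intercepts also remove the between-diagnosis part of the predictor. With six groups, a true common slope of 0.6 (r about 0.6) and no other diagnosis effect, power falls from 84% to 70% if the predictor does not vary by diagnosis. It falls from 80% to 44% if diagnosis explains half of the predictor's variance.

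**The case against.** The strongest reply is that the protocol never says the regressions are pooled or unadjusted. It says only that they are linear, and covariate terms are often left to an SAP, which is not at hand. This stands as far as it goes: pooling is an inference from the absence of a diagnosis term. What remains is that the protocol commits to stratification, once inside its own analysis section, and gives it no use in the analysis it then fixes.

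Second, the secondary aim concerns cholestatic patients as a population, enrolment is deliberately regardless of cause, and the proposed mechanism is not specific to one disease. Cholesterol differences between diagnoses are then legitimate variation in exposure, and a crude slope is a valid answer to the aim as worded. This also stands. The rejection rates in Step 2 are too high only for the hypothesis of no relation within diagnoses, which the protocol does not state.

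Third, the protocol's warning about small groups might be thought to cover the point. It does not: it concerns comparisons within the cholestatic population and says nothing about what drives a slope across all patients.

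A reader might also infer that the 20 observations are not independent and that the planned p-values are therefore wrong. The documents do not support that. The design is cross-sectional with one sample per patient, and correlation through diagnosis arises only if diagnosis effects are treated as random, as in the simulation. Nor do they support a rule that a relation may be claimed only if the adjusted slope is significant. Step 4 shows that such a rule could discard real signals in a pilot.

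**Conclusion.** The point holds as a gap between a stated design feature and the stated analysis. Without a diagnosis term the slopes are crude associations and should be read as such. How misleading they could be for the within-diagnosis question depends on quantities the protocol does not give. With six groups, the nominal 5% test rejects about 6-7% of the time at shares of 20-30% in both variables and about 11-19% at 50-70%. Fewer, larger groups give somewhat higher rates. At 10%, or if only one variable differs by diagnosis, there is no material inflation. The comparison of patients with controls, which serves the primary aim, is not affected. This is a moderate, easily corrected weakness in the secondary analysis of a pilot.

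**What to change.** In Section 9 (Statistical analysis):

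- Keep the slope across all patients and label it a crude association.
- Beside it, as a sensitivity analysis, report a common slope with a separate intercept for each diagnosis, with its confidence interval.
- Mark diagnosis on the scatter plots, and do not fit separate regressions in strata of 3-5.
- Describe a relation as independent of diagnosis only if the two slopes agree in direction and size, without requiring the adjusted slope to be significant.

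The extrahepatic/intrahepatic distinction should not be borrowed to merge small categories. The protocol uses it to define cholestasis and does not assign every listed diagnosis to a side.

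The change is to wording and analysis only. Diagnosis must be known anyway for the promised stratification, so no extra patients or samples are needed. The cost is precision in the adjusted slope: up to 5 degrees of freedom (18 - 13), plus the loss of between-diagnosis variation in the predictor. That is why it should stand beside the pooled slope and not replace it.

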### **Disease Cohort**

Age greater than one year old  
Direct bilirubin level of >2 mg/dl.  
No known congenital red cell membrane defect

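### The regressions of Omin and Elmax on the laboratory markers name no age term, and age matching protects only the patient-control comparison; an age-adjusted slope should be reported beside the crude one

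*Protocol*

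**What the plan says.** - **Model.** Section 9, Statistical analysis, says that the ektacytometry values, mainly Omin and Elmax, "will be correlated with direct bilirubin levels, serum cholesterol levels and vitamin E levels by linear regression analysis". Outcomes, predictors and method are named. No covariate is named, and none is ruled out.
- **Population.** The Secondary Aims ask how far laboratory abnormalities "in cholestatic patients are related to changes in red blood cell ektacytometry in this patient population". The Objective in the Abstract likewise ties the correlations to the patients' own laboratory levels. The Statistical analysis section does not itself say that the regressions are run within patients; that follows from these two places.
- **Age range.** The Disease Cohort criterion is "Age greater than one year old". The upper limit stands in Section 7 on consent, not among the eligibility criteria: "All patients will be under the age of 18 years old".
- **Where age is handled.** Controls are to be "Age matched to disease cohort", and children under one are excluded from both groups.
- **Age is collected.** Section 8 lists "current age at time of blood draw" among the recorded items.
- **Size.** "The sample size of 20 cholestatic patients and 20 controls is estimated based on the number of patients followed at CCHMC". The same section states that no power analysis could be done.

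**The concern.** Age matching balances age between patients and controls, which serves the primary aim. The secondary aim is answered by slopes among the 20 patients, where matching has no effect. As written, then, a variable that the design controls in one comparison goes unmentioned in the other, although it is in the database.

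If younger and older children differ both in, say, cholesterol and in Omin, a crude slope mixes the cholesterol relation with the age relation. When the two age relations push in the direction of a slope, one can appear where there is none. When they oppose a real slope, they can hide it. The protocol intends its data to inform later studies, so a distorted slope could be carried forward.

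**Working it through.** **Figure to reproduce.** None. The sample size rests on feasibility, and no alpha, effect size or standard deviation is given for the regressions.

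**Inputs.** From the protocol: n = 20 patients, one marker per regression, age available. Assumed: two-sided 5% test, normally distributed standardised variables, and the age correlations, which the documents do not give and which are therefore varied.

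**Model.** Outcome y = b·x + c·age + error, where x is the marker and ρ is the correlation of x with age. The expected crude correlation is b + c·ρ. With b = 0 it is c·ρ, the product of the two age correlations.

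**What a crude correlation must reach at n = 20.** Critical |r| = t/√(18 + t²) with t = 2.101, which gives 2.101/√22.41 = 0.44. For 80% power, by Fisher's z, r = tanh((1.960 + 0.842)/√17) = tanh(0.680) = 0.59.

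**No true relation (b = 0), 40,000 simulated data sets per row.**

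| Marker-age and outcome-age correlation | Expected crude r (product) | Rejection, crude | Rejection, age-adjusted |
|---|---|---|---|
| 0 and 0 | 0 | 4.8% | 4.8% |
| 0.2 and 0.2 | 0.04 | 5.3% | 5.1% |
| 0.3 and 0.3 | 0.09 | 6.5% to 6.7% | 5% |
| 0.4 and 0.4 | 0.16 | 10% | 5% |
| 0.5 and 0.5 | 0.25 | 19% | 5% |
| 0.6 and 0.6 | 0.36 | 36% | 5% |
| 0.7 and 0.7 | 0.49 | 62% | 5% |

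The two values at 0.3 come from separate runs and differ by simulation error. If age is related to only one side (0.5 with the marker and 0 with the outcome, or the reverse), the crude rate stays at about 5%.

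**Masking (true b = 0.5).** With ρ = -0.5 and c = +0.5, the expected crude r is 0.5 - 0.25 = 0.25, and power is 18% crude against 51% adjusted. With ρ = -0.3 and c = +0.3, it is 0.5 - 0.09 = 0.41, and power is 45% against 58%.

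**Price of adjusting (true b = 0.5).**
- Age unrelated to marker and outcome: power 64% crude, 62% adjusted.
- Age related to the marker at 0.5 but not to the outcome: 64% crude, 51% adjusted. The standard error grows by about 1/√(1 - 0.5²) = 1.15.
- Age unrelated to the marker but with an outcome effect of 0.5: 64% crude, 78% adjusted.

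Residual degrees of freedom fall from 18 to 17.

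**The case against.** The strongest objection is that the Statistical analysis section is silent on covariates and does not fix an unadjusted model. Linear regression can carry an age term, and covariate lists are commonly left to a statistical analysis plan, which is not shown. This stands: a reader might infer that the protocol commits to a wrong model, and the text does not support that. What remains is a suggestion to name one covariate that is already collected and that the design already controls elsewhere.

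A reader might also infer that the crude p-values will be too small. That needs age to be related to both the marker and the outcome, in the direction that creates a slope. No section states either relation. Age matching and the exclusion under one year suggest at most that the investigators thought age might matter, and no reason is given for the exclusion. The exclusion is also a limited form of age control within the patient group, so age is not wholly unhandled there.

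Two further points have weight. The aim asks about association, which a crude slope answers as worded, so the adjusted slope should accompany it and not replace it. Diagnosis could confound as well, and the protocol plans to stratify by it without tying this to the regressions. With only 3 to 5 patients expected per diagnosis, however, diagnosis terms would use several degrees of freedom, whereas age uses one.

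**Conclusion.** The point holds as a low-severity improvement. No age term is stated, the patients span just over 1 to under 18 years, and matching cannot protect slopes estimated within patients. Whether this matters depends on age relations that the documents do not give. The bias is negligible if both correlations are 0.2 or below, small at 0.3, and material from about 0.5 on both sides, where the crude test rejects a true null about 19% of the time. These figures assume n = 20, linear relations, normality and equal correlations on the two sides. They show what is possible and do not predict what this cohort will show. The documents do not support calling this a contradiction, a wrong figure or a demonstrated bias.

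**What to change.** In Section 9, Statistical analysis, state that each regression of Omin and Elmax on a laboratory marker is run within the cholestatic patients and reported twice, crude and adjusted for age at blood draw, each slope with its 95% confidence interval. Add that a relation will be interpreted as independent of age only if it persists after adjustment.

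This takes about two sentences of text and no new data. It costs one residual degree of freedom, and the adjusted slope will have a wider interval if age tracks the marker but not the outcome. Showing both slopes lets the reader see that loss.
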